5.6.3.2. Vital Signs and Physical Examination Findings

The following parameters measurements will be analyzed:

- Supine pulse rate (bpm)
- Supine systolic blood pressure (mmHg)
- Supine diastolic blood pressure (mmHg)
- Body temperature ($^{\circ}\text{C}$)

The abnormalities in vital signs will be determined according to the criteria specified in the Cardiovascular Safety – Abnormalities Table (see Clinical Protocol Appendix 7).

An assessment is Treatment Emergent (TE) if abnormality worsened as compared to the abnormality at baseline; this also includes the shift from abnormally high to abnormally low and vice-versa. Post-baseline abnormalities are always treatment-emergent with regard to missing abnormalities at baseline. The abnormally high values (i.e., abnormally high, grade 1 or mild, grade 2 or moderate, grade 3 or severe) versus the abnormally low values are considered equally important.

For each parameter, a “worst-case” analysis will be performed by using the worst abnormality and time point per participant. Worst-case will be derived within each phase, including unscheduled assessments. In case the same subject has both abnormalities (low and high) for the same test within the same phase, the participant will be counted in the analysis for both abnormality directions (abnormally high and low).

Vital signs records with partial dates (any of day/month/year is missing) will not be used in the analysis but will be listed.

Descriptive statistics of continuous vital sign parameters and body temperature will be calculated for observed values and changes from baseline at each scheduled time point.

Shift tables will be provided summarizing the shift in vital sign and body temperature values from baseline over time with respect to abnormality criteria (low, normal, high) for each parameter by study phase.

A cross-tabulation of the worst abnormalities versus baseline per parameter and study phase will be presented including also the number of participants per abnormality, the number of participants with treatment emergent abnormalities per abnormality.

A tabulation of percentage and number of the participants who have treatment-emergent worst abnormalities per parameter and study phase will be included.

A listing including all parameters for participants with at least one treatment-emergent abnormality (on actual values or change from baseline) will be provided. Additional vital signs assessments corresponding to the rash eCRF pages will be only listed as applicable.

The physical examination findings and abnormalities will be listed.

5.6.3.3. *Electrocardiogram*

Evaluation of the triplicate 12-lead ECGs will be based on the mean value of the triplicate parameters and the abnormalities will be defined on the triplicate means.

The following ECG parameters measurements will be analyzed:

- PR interval (ms)
- Heart Rate (bpm)
- QT interval (ms)
- QRS duration (ms)
- QTc Corrected (Fridericia's formula QTcF)

Fridericia's formula: QTcF (msec) = QT (msec) / (RR (msec)/1000)^{1/3}; if RR is missing, use QT (msec) * (HR(bpm)/60)^{1/3}; The abnormalities in ECG parameters will be determined according to the criteria specified in the Cardiovascular Safety – Abnormalities Table (see Clinical Protocol Appendix 7, Cardiovascular Safety- Abnormalities Table). Abnormalities on actual values are provided for HR, PR, QRS and QTcF. Additional abnormalities on change from baseline will be provided for QTcF. No abnormalities will be defined for actual uncorrected QT values. Uncorrected QT \geq 500 ms will be flagged and only shown in listings.

An assessment is TE if abnormality worsened as compared to the abnormality at baseline; this also includes the shift from abnormally high to abnormally low and vice-versa. Post-reference abnormalities are always TE with regard to missing abnormalities at baseline. The abnormally high values (i.e., abnormally high, borderline prolonged, prolonged, pathologically prolonged) versus the abnormally low values are considered equally important. Abnormalities defined on changes from baseline are always TE.

For each parameter, a “worst-case” analysis will be performed by using the worst abnormality and time point per participant. Worst-case will be derived within each phase, including unscheduled assessments. In case the same subject has both abnormalities (low and high) for the same test within the same phase, the participant will be counted in the analysis for both abnormality directions (abnormally high and low).

For the time points on which triplicate ECGs apply, a rounded mean value to the next integer per triplet will be calculated per time point before any further handling. This rounded mean value will be used through the entire analysis also in case of 1 or 2 missing values.

ECG records with partial dates (any of day/month/year is missing) will not be used in analysis, except in the listings. The following imputation rules will be applied.

If heart rate (HR) is missing, it will be calculated using RR (if available) and rounded to the integer value (see formula below) before any further handling if applicable.

$$\frac{1000}{RR(ms)} = \frac{HR(bpm)}{60}$$

HR from the vital signs section (i.e., pulse) will not be used in this ECG analysis section. RR values (if available) will only be listed. Recalculated HR values will be flagged.

Descriptive statistics will be calculated for observed values and changes from baseline per parameter (all parameters except for RR) at each scheduled time point by study panel and analysis phase.

Shift tables will be provided summarizing the shift in ECG values from baseline over time with respect to abnormality category (low, normal, high) for each parameter by study phase.

A cross-tabulation of the worst abnormalities (on actual values) versus baseline per parameter by study phase will be presented including also the number of participants per abnormality. A tabulation of number and percentage of the participants who have TE worst abnormalities per parameter (i.e., for HR, PR, QRS and QTcF) and study phase will also be presented.

A cross-tabulation of the worst change from baseline abnormalities (i.e., for QTcF) versus the baseline category per parameter will be presented by study panel and study phase.

Frequency tabulations of categorized corrected QT/QTc change from baseline (<=30 msec, >30- <=60 msec, >60 msec) and categorized corrected QT/QTc interval values (<=450 msec, >450- <=480 msec, >480- <= 500 msec, >500 msec) per timepoint will be presented by study panel.

Listings including all parameters for participants with at least one treatment-emergent abnormality (on actual values or change from baseline), including all findings (e.g., interpretation, rhythm, or technical findings) for participants with uncorrected QT values ≥ 500 ms will be provided separately.

5.7. Other Analyses

5.7.1. Pharmacokinetics

Two types of plasma PK analyses will be conducted, including noncompartmental analysis in the PK sub-study participants (Section 5.3.2.2) and population PK analysis in all participants. Details of the plasma PK analyses will be described in a separate analysis plan and results will be reported separately.

5.7.2. Pharmacokinetic/Pharmacodynamic Relationships

Relationships of plasma PK parameters for JNJ-73763989 (JNJ-73763976 and JNJ-73763924), and optionally of JNJ-56136379, NA, and PegIFN- α 2a, with selected efficacy and with selected safety endpoints will be evaluated and graphically displayed, if applicable.

Modeling of key pharmacodynamic parameters (e.g., HDV RNA, HBsAg) may be performed using population pharmacokinetics/pharmacodynamics (PK/PD). Details will be described in a population PK/PD analysis plan and results of the PK/PD analysis will be presented in a separate report.

5.7.3. Viral Genome Sequence Analysis

Viral genome sequence analysis may be performed to identify pre-existing baseline polymorphisms and to evaluate emergence of genetic variations (including substitutions) associated with JNJ-56136379, JNJ-3989, and/or ETV or TD treatment on both nucleotide and/or amino acid level.

The sequencing of samples may be triggered by the sponsor virologist based on changes in HBV DNA levels observed in each individual participant and the limits of the sequencing assay.

Virology results will be presented by specified timepoints and genetic region and position of interest. A separate virology report may be prepared.

5.7.4. Definition of Subgroups

Table 6: List of Subgroups of Interest for Efficacy and/or Safety Purpose

Subgroup	Purpose	Definition
Sex	Efficacy, Safety	Male, Female
Age Group	Efficacy, Safety	≤ 45 years, > 45 years
Race	Efficacy, Safety	Asian, Non-Asian
Body Mass Index	Safety	≤ 25 , $>= 25$
HBsAg level at baseline	Efficacy	<1000 vs. $>=1000$ $<10,000$ vs. $>=10,000$
Type of NA at Study Entry	Safety	TD, TAF
Received PegIFN- α 2a (Optional)	Efficacy, Safety	Yes/No
HBsAg % Positive Cells	Efficacy	$<$ Median vs. $>=$ Median Value

This list of subgroups may be modified based on interim/final results and clinical interest.

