5.5.1, Table 4 List of Intrahepatic and Blood Markers of Interest	Removal of some intrahepatic markers and endpoints.	The data was not collected because of various issues with laboratory processing.
5.5.2 Association Between Baseline Characteristics or Intrahepatic/Blood Markers with Efficacy Variables	Added some intrahepatic markers and removed others.	Revised list to be consistent with actual data that was collected.
6.3.2, Table 9 Baseline Characteristics Variables	Removed several intrahepatic markers and added description to analysis	Revised list to be consistent with actual data that was collected.
5.7.4 Definition of Subgroups	Revised definitions of subgroups used in analysis of efficacy and safety outcomes.	The definitions for the subgroups have been revised according to discussions with the clinical team. Thresholds for the subgroups have also been defined, based on interim analysis of subject data.
5.4.2.4.1.2 Change from Baseline to Nadir	Removed analysis	Clinical team decided that this analysis was no longer relevant.

Amendment 1

Overall rational for Amendment 1: This administrative amendment incorporates additional clarification on endpoints, data handling rules, on-treatment and off-treatment definition that have previous been documented in the Data Presentation Specification for past interim analysis.

Clarifications, Additions, Corrections		
Section Number and Name	Description of Change	Rationale
5.1.3 On-Treatment and Off-Treatment Period	Added definition for the on-treatment and off-treatment period.	Previous logic did not account for different end of the on-treatment period based on the last study agent.
5.1.5 Data Handling Rules	Revised ULOQ and Imputed Values data cutpoints for HBsAg, HBeAg and HBcrAg. Updated guidelines for the imputation of HBV DNA.	Improved language for clarity and precision.
5.1.6 Analysis Specifications	Added to text to avoid time-to-event and subgroup analyses in case that there are not enough data.	Improved language for clarity.
5.3.1.2.4.2 Multiple Imputation	Reduced the number of imputed datasets to 20.	Number of imputed datasets was reduced due to limited missing data.
5.4.1.2 Intrahepatic Viral Parameters	Added the analysis of Intrahepatic HBcAg.	Added endpoint which was not included in the previous version.

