5.1.7. Level of Significance

Due to the exploratory nature of this study, no formal statistical test will be performed. Two-sided 80% CI will be provided with the summary statistics. No adjustment for multiple CIs will be made.

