5.3.1.3. Subgroup Analyses

The potential association between the primary endpoint and baseline characteristics (Appendix 3) may be explored graphically using forest and scatter plots. The baseline subgroups of interest for efficacy are defined in Section 5.7.4.

The potential association between the primary endpoint and treatment-related characteristics may be explored both by using summary tables and plots. Subgroups in this category include:

- Received at least 1 dose of JNJ-6379 (No / Yes);
- Treatment with PegIFN- α 2a during study (No / Yes / Yes for 12 weeks / Yes for 24 weeks).

5.3.2. For Panel 3

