- Proportion of participants with HBsAg <10 IU/mL at Week 40 (Yes/No)
- Proportion of participants with HBsAg <10 IU/ml at Off-Treatment Week 24 (Yes/No)
- Proportion of participants with HBsAg Seroconversion at Off-Treatment Week 24 (Yes/No)
- Proportion of participants with Functional Cure at Off-Treatment Week 24 (Yes/No)

For each of the endpoints listed above, the potential association with the following selection of characteristics or intrahepatic/blood markers may be assessed:

- Duration of NA (years)
- Age (years)
- Duration of infection (years)
- Baseline HBeAg level (quantitative), for panel 1 only
- Baseline HBV DNA level (\log_{10})
- Baseline ALT Level (quantitative)
- Baseline Peripheral HBsAg level (\log_{10})
- Baseline Number of HBsAg+ hepatocytes (\log_{10})
- Proportion of HBsAg+ hepatocytes at baseline
- Proportion of cccDNA-positive hepatocytes at Baseline
- Proportion of pgRNA-positive hepatocytes at Baseline
- HBeAg level (quantitative) at Week 40

- HBV DNA level (\log_{10}) at Week 40
- ALT Level (quantitative) at Week 40
- Peripheral HBsAg level (\log_{10}) at Week 40
- Proportion of HBsAg+ hepatocytes (\log_{10}) at Week 40
- Proportion of cccDNA-positive hepatocytes at Week 40
- Proportion of pgRNA-positive hepatocytes at Week 40

These lists may be modified based on clinical relevance and data availability.

For Panels 1 and 2, logistic regression models will be performed for each efficacy endpoint of interest, and will include study panel and characteristics/marker of interest as factor, with and without the study panel-by-baseline variable as the interaction-terms. Covariates and/or interaction terms may be added or removed to a given model for fitting purpose.

Odd-Ratios (OR) and corresponding 80% CIs will be also calculated without multiplicity adjustment overall. Statistical analysis of treatment heterogeneity between subgroups will be conducted by assessing the significance of the interaction term. The forest plot will present graphically the on/off treatment efficacy OR estimate and its 80% CI resulting from the model by the prespecified subgroups on the overall population and by study panels.

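### SAP 5.5.2 calls its forest-plot subgroups prespecified, but thresholds were set from interim data on the same participants and the list may still change on final results

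*SAP*

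**What the plan says.** Three statements in the SAP bear on this point.

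- **Origin of the thresholds.** The version history gives, as part of the reason for the Amendment 2 revision of 5.7.4: "Thresholds for the subgroups have also been defined, based on interim analysis of subject data".
- **Status of the list.** Under Table 6 in 5.7.4: "This list of subgroups may be modified based on interim/final results and clinical interest".
- **Label on the output.** SAP 5.5.2 plans a forest plot of odds ratios with 80% CIs "resulting from the model by the prespecified subgroups on the overall population and by study panels".

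Section 5.5.2 does not cite Table 6 beside that label. Table 6 is nevertheless the SAP's list of baseline subgroups, and 5.3.1.3 points to it for the primary endpoint: "The baseline subgroups of interest for efficacy are defined in Section 5.7.4". Those primary-endpoint associations "may be explored graphically using forest and scatter plots" and are not called prespecified.

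On inference, 5.1.7 says "Two-sided 80% CI will be provided with the summary statistics" and "No adjustment for multiple CIs will be made".

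Table 6 also splits BMI, a safety-only subgroup, at 25 or below versus 25 or above.

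**The concern.** A prespecified subgroup is one defined before anyone could see how results differ across it. Readers give such a subgroup more weight than one found in the data. Here the thresholds follow interim data from the same people, and the list may change once final results are known. The label claims a property that the subgroups do not have.

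This matters because Protocol 2.1 includes among the study's aims the identification of subpopulations with a particular response. SAP Attachment 1 expects only 9 to 10 participants per panel with usable primary data, so chance differences between subgroups will be large. If a cut-off was chosen because it separated outcomes well, the plotted interval ignores that choice and is too favourable.

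**Working it through.** **Step 1. Can the label be reconciled with the rest of the SAP?** The log entry explains the current Table 6, so it cannot be set aside as a description of superseded text. Thresholds taken from interim data were not specified before the data, and a list open to change on final results is not fixed. The label therefore fails on the wording alone.

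**Step 2. Could outcomes have guided the cut-offs?** The study is open-label. SAP 5.8 has the sponsor perform the interim analyses, without a data monitoring committee, and Table 7 includes secondary efficacy and exploratory endpoints from the first interim analysis onward. The rationale for Amendment 1 refers to a past interim analysis, so one predates Amendment 2. Outcomes could have been used. No passage says that they were.

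**Step 3. How large could the effect be?** The SAP gives no error rate for subgroup analyses, so there is no figure to reproduce. The range was simulated.

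Inputs from the documents:
- Two-sided 80% CI, so the nominal chance of excluding the null is 1 − 0.80 = 0.20.
- Target of 24 in Panels 1 and 2. With 20% dropout, 24 × 0.8 = 19.2, taken as 20.

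Assumptions not in the documents:
- 2, 3 or 5 candidate cut-offs per marker.
- Correlation ρ between the outcome used to choose the cut-off and the final outcome, from 0 (choice ignores outcomes) to 1 (choice made on the final outcome).

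Method: there is no true effect, the outcome is continuous and normal, and the CI is a pooled-t 80% interval. The cut-off with the largest |t| on the choosing outcome is kept and then analysed on the final outcome in the same participants. Each cell has 6,000 runs, with Monte Carlo standard error near 20% of √(0.2 × 0.8 / 6000) = 0.005.

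Share of 80% CIs excluding the null, n = 20:

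| Candidate cut-offs | ρ = 0 | ρ = 0.5 | ρ = 0.8 | ρ = 1 |
|---|---|---|---|---|
| 2 | 0.210 | 0.231 | 0.283 | 0.325 |
| 3 | 0.204 | 0.257 | 0.353 | 0.448 |
| 5 | 0.199 | 0.278 | 0.410 | 0.556 |

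A single fixed cut-off gives 0.206. At ρ = 1, n = 24 gives 0.342, 0.449 and 0.545, and n = 12 gives 0.339, 0.443 and 0.589, so the pattern depends little on n. With five candidates and n = 20, the mean absolute spurious difference is 0.41 SD at ρ = 0, then 0.47, 0.59 and 0.72 SD.

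**Step 4. What would remain after a fix?** Table 6 has seven efficacy splits: sex, age, race, HBsAg at 1,000, HBsAg at 10,000, PegIFN-α2a, and percentage of HBsAg-positive cells. If they were independent, the chance that at least one unadjusted 80% CI excludes the null is 1 − 0.8⁷ = 0.79, with 7 × 0.2 = 1.4 expected. SAP 5.1.7 discloses that no adjustment is made, and correcting the label does not change this.

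**Step 5. BMI.** As Table 6 reads, a BMI of exactly 25 belongs to both groups. Table 8 places 25 in the upper category only.

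**The case against.** A reader might infer that the subgroup effects *are* overstated and that the cut-offs were result-driven. The documents do not support that, and most of the case against it stands.

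- The log says only that interim data were used. Choosing cut-offs from baseline distributions or group sizes fits that statement equally well, and the ρ = 0 column shows it leaves the rate near 20%.
- Table 6 does not look like a search for the best cut-point. Sex, race and PegIFN-α2a have no numerical threshold. Age 45 is already a boundary in Table 8, and HBsAg 1,000 and 10,000 are already baseline categories in Table 9. The split on HBsAg-positive cells is at the sample median, which uses no outcome if it refers to baseline, as 5.3.1.3 implies.
- Listing two HBsAg cut-offs does not mean reporting the better one. The SAP nowhere plans a best-of-several search, and the 5.5.2 endpoints are binary with logistic odds ratios, so the simulated rates are illustrative.
- A reader might also take the label to cover every subgroup plot. It appears for the 5.5.2 forest plot only.
- The study is openly exploratory, with no hypothesis and unadjusted intervals.

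The last point does not rescue the label. Exploratory status excuses wide, unadjusted intervals, but it does not make a list prespecified when it follows interim data and can change on final results. Section 5.5.2 also assesses the significance of an interaction term although 5.1.7 rules out formal testing, so the exploratory framing is not kept throughout.

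**Conclusion.** The point holds as a matter of labelling and transparency. The word prespecified in 5.5.2 is not supported by the Amendment 2 log or by the sentence under Table 6. Subgroup differences *could* be overstated, depending on something the documents leave unstated: whether outcomes guided the cut-offs.

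For one marker under no true effect, the hypothetical chance that an 80% CI excludes the null is about 20% if the choice ignored outcomes, 23–41% at ρ = 0.5 to 0.8, and 33–56% if the choice was made on the final outcome. These figures rest on the assumed 2 to 5 candidate cut-offs, n = 20 and a continuous outcome.

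The consequence is confined to exploratory output. No primary conclusion or decision rule depends on it, and the point is minor. The BMI overlap is a separate slip in a safety subgroup and adds nothing to the efficacy argument.

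**What to change.** 1. In SAP 5.5.2, delete the word prespecified, or list which subgroups predate the interim data.
2. Replace the sentence under Table 6 with: *Table 6 is fixed as of Amendment 2; numerical cut-offs set after interim data are identified as such with the data used to choose them; any later subgroup or cut-off is labelled post hoc and all cut-offs examined are shown.* This wording leaves sex, race and PegIFN-α2a unmarked, since they have no cut-off to choose.
3. Set the BMI safety subgroup to <25 versus ≥25, matching the boundary in Table 8, after checking the signs in the source file.

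No new model is needed. Section 5.5.2 already lists baseline HBsAg on the log10 scale and includes study panel in the logistic models.

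The cost is SAP wording only. The downside is less freedom to add or move subgroups without a post hoc label.

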5.8. Interim Analyses

Two Interim Analyses (IA) may be performed: when all participants have completed Week 20 in the study intervention phase (or discontinued earlier) and when they have completed Week 72 (FU Week 24) in the follow-up phase (or discontinued earlier). These IAs will be performed by the sponsor to support interactions with health authorities, as well as to support internal decisions about additional studies and/or investigation of other combination regimens.

Both primary (when all participants have completed Week 48 or discontinued earlier) and interim analyses will be based on all data available at the predefined cut-off time points and may include data at later time points for those participants who have reached subsequent visits.

The final analysis will be performed when all participants have completed the last study visit (Follow-up Week 48) or discontinued earlier.

The overview of data domains and specific endpoints that will be provided for each analysis is presented in [Table 7](#).

Table 7: Overview of Times of Data Summaries and Analyses at Planned Interim, Primary and Final Analyses

	IA1 when all participants have completed Week 20	Primary Analysis when all participants have completed Week 48	IA2 when all participants have completed FU Week 24	Final Analysis when all participants have completed FU Week 48
DATA DOMAINS FOR ANALYSIS				
Subject Information				
Baseline & Demographic characteristics	X	X	X	X
Disposition and Study Populations	X	X	X	X
Extent of Exposure	X	X	X	X
Safety				
TEAEs, SAEs, AE of interest, fatal AEs, AEs causing treatment discontinuation	X	X	X	X
Laboratory Tests	X	X	X	X
ECG	X	X	X	X
Vital signs	X	X	X	X
Efficacy				
Primary efficacy endpoints		X	X	X
Secondary efficacy endpoints	X	X	X	X
Exploratory Endpoints	X	X	X	X
PK		X	X*	X*
Virologic breakthrough HBV	X	X	X	X
Flares: Viral, Biochemical, Clinical	X	X	X	X
Viral Genome Sequence Analysis		X	X	X

* If new data are available.

No DMC or Data Review Committee (DRC) is required for this study.

An Independent Flare Expert Panel (IFLEP) is appointed for this study to monitor ALT flares and make recommendations regarding flare management based on analysis of aggregate data. The IFLEP is composed of 3 independent medical experts with experience and expertise in hepatitis B and its treatment.

Further details on the IFLEP process will be provided in the IFLEP charter.

